1.0 Study Summary

Study Title	ICG fluoresce imaging in lower extremity amputation patients	
Study Design	Prospective nonrandomized trial	
Primary Objective	Evaluate changes to bone perfusion in association with osteotomy and soft tissue stripping in patients undergoing lower extremity amputation	
Secondary	None	
Objective(s)		
Research	ICG contrast infusion and ICG-based fluorescence imaging	
Intervention(s)/		
Investigational		
Agent(s)		
IND/IDE #	NA	
Study Population	Patients undergoing lower extremity amputation	
Sample Size	30 patients	
Study Duration for	During surgical procedure only	
individual		
participants		
Study Specific	AE: adverse event/adverse experience	
Abbreviations/	5	
Definitions	CT: computed tomography	
	CRF: case report forms	
	DCE-FI: dynamic contrast enhanced fluorescence imaging	
	DHMC: Dartmouth-Hitchcock Medical Center	
	GDP: Good Clinical Practice	
	ICG: indocyanine green	
	Imx: maximum ICG fluorescence intensity	
	LAR: legally authorized representative	
	SAE: serious adverse event/serious adverse experience	
	SOP: standard operating procedure	

2.0 Objectives*

Specific Aim 1: Identify bone perfusion kinetics at baseline and following osteotomy and subsequent soft tissue stripping in patients undergoing scheduled lower extremity amputation.

Hypothesis 1—Human bone perfusion kinetics will demonstrate predictable and reproducible changes when undergoing vascular compromise, osteotomy, and soft tissue stripping.

Specific Aim 2: Optimize image data processing and identify ICG-based DCE-FI kinetic curve properties most closely associated with low bone perfusion.

Hypothesis 2—Low post-debridement bone perfusion is associated with higher rates of infection.

3.0 Background*

Infection following high-energy trauma or blast injury is one of the most challenging complications facing musculoskeletal trauma patients, with an estimated annual cost of \$35 billion in the US (https://stacks.cdc.gov/view/cdc/11550). Infection can be catastrophic, potentially causing prolonged morbidity, reduced function, permanent disability and amputation. Failed treatment results in chronic bone infection requiring repeat surgical procedures in approximately 30% of patients. 1-4

Blood supply plays a critical role in the bone health for trauma patients by delivering necessary oxygen, nutrients, antibiotics, and immune cells necessary to treat infection successfully, 5-9. The management of trauma-related infection is therefore based on **aggressive**, **thorough debridement** of all poorly perfused bone and connective tissue, followed by fracture stabilization to prevent further injury. More extensive debridement is believed to improve treatment success; however, additional tissue loss requires increasingly complex reconstructive procedures to fill bone and connective tissue voids. **At present there are no objective, intraoperative, and real-time techniques to assess bone perfusion and thoroughness of debridement.** This unmet clinical need results in substantial practice variation and places patients at unnecessarily high risk for chronic infection and potentially avoidable surgical procedures.

Our multidisciplinary research team has demonstrated that quantitative indocyanine green (ICG)-based Dynamic Contrast Enhanced Fluorescence Imaging (DCE-FI) can assess bone perfusion in a measurable, reproducible and predictable way using a porcine model. ¹⁰ Furthermore, we have initiated an Institutional Review Board (IRB)-approved protocol to perform similar imaging in human trauma patients with good success. To this end, the primary objective of this project is to gather critical pilot data that will accelerate translation of ICG-based DCE-FI to clinical practice for human trauma patients. During this translational work we will systematically develop and evaluate an ICG-based DCE-FI methodology and analytic tools for intraoperative assessment of bone perfusion. Our long-term goal is to apply these sophisticated methods to guide surgical debridement that will enhance trauma patients' short- and long-term recovery.

[figure not shown]
4.0 Study Endpoints*

Primary outcome measure is ICG-based DCE-FI changes that occur as a result of osteotomy and soft tissue stripping associated with the amputation.

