11.0 Local Number of Subjects

The primary outcome measure is total bone blood flow (TBBF). Informed by data collected from the porcine study, a total sample size of 30 trans-tibial amputation patients is required to determine the difference in TBBF baseline bone perfusion kinetics and change in the bone perfusion kinetics associated with osteotomy and subsequent soft tissue stripping. Considering that the controlled environment associate with the porcine model may not be replicated to the same degree in the amputation sample, a more conservative difference of 0.84 standard deviations between baseline and osteotomy and soft tissue stripping was selected (i.e., 50% of the effect size identified in the porcine model). Assuming a one tailed test, a Type I error rate of 0.05, and a Type II error rate of 0.80, a sample of 20 was determined with an additional 10 amputation patients recruited in the event that there is any protocol- or data-related issues. Data analysis will be performed after half of the patients are enrolled to re-calculate sample size needed to determine a difference.

We anticipate that 20 subjects will be accrued locally. We anticipate that 20 patients will be enrolled at Brigham and Women's Hospital. A total of 40 patients will be enrolled.

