14.0 Risks to Subjects*

Risk of ICG injection: ICG (Indocyanine Green) will be administered intravenously three times: once after exposure, once after osteotomy and once after soft tissue stripping. ICG is FDA approved for human use in angiography for ophthalmology and cardiology applications and is given routinely to patients in these clinical settings. The risks are considered minimal and consist of nausea, vomiting, hives, increased heart rate in subjects with particular sensitivity to the dye. ICG does contain sodium iodide and patients with a history of allergy to iodides will be excluded. Anaphylactic or urticardial reactions are rare but have been reported in patients both with and without a history of allergy to iodides. Anaphylactic deaths have been reported following IGG administration during cardiac catheterization. Reported rates of mild, moderate and severe adverse reactions to ICG are 0.15%, 0.2% and 0.05%. Every effort will be made to minimize this risk as much as possible. It is the standard of care at this institution to obtain information related to allergies, sensitivities and past medical histories upon patient arrival. Patients will also be monitored throughout their hospitalization, as is the standard of care, by everyone involved in their medical care for evidence of new or previously unknown reactions or sensitivities. Additionally, at all times ICG fluorescence imaging assessments are taking

place, research staff and both surgical and anesthesia staff will monitor patients closely for any adverse reaction to ICG. Research staff and surgical and anesthesia staff will also monitor patients for at least 30 minutes after all ICG fluorescence assessment procedures have been completed. In the event of an unexpected allergic reaction, Dartmouth-Hitchcock Medical Center and all affiliated groups within this institution have procedures in place for managing patients with unknown or unexpected allergic reactions. If such a reaction were to occur, all standard of care treatments will be provided including but not limited to treatment with appropriate agents such as epinephrine, antihistamines and corticosteroids. Risk of infection from IV injection is also extremely rare but can occur. Pregnant women are excluded from the study. A pregnancy test is administered to women of child-bearing age on request at no cost.

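### Do Sections 4.0 and 11 leave the primary outcome, the image pair and the direction of the one-tailed test too open?

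*Protocol*

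**What the plan says.** Section 4.0 defines the outcome by imaging method: "Primary outcome measure is ICG-based DCE-FI changes that occur as a result of osteotomy and soft tissue stripping associated with the amputation". Section 11 defines it by metric: "The primary outcome measure is total bone blood flow (TBBF". TBBF appears nowhere else in the protocol. The abbreviation list in Section 1.0 carries one fluorescence parameter, "Imx: maximum ICG fluorescence intensity", which is not used again.

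Imaging follows three injections (Sections 6.7 and 14.0): "once after exposure, once after osteotomy and once after soft tissue stripping". For the sample size, Section 11 states that "a more conservative difference of 0.84 standard deviations between baseline and osteotomy and soft tissue stripping was selected", and continues "Assuming a one tailed test" with a type I error of 0.05. It arrives at 20 patients and adds 10 for protocol or data problems. Sections 11 and 25.0 also give a two-site total of 40. Section 11 plans a data analysis at half enrolment to recalculate the sample size.

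The objective in Section 1.0 is non-directional: "Evaluate changes to bone perfusion in association with osteotomy and soft tissue stripping in patients undergoing lower extremity amputation". So is Hypothesis 1 in Section 2.0: "Human bone perfusion kinetics will demonstrate predictable and reproducible changes when undergoing vascular compromise, osteotomy, and soft tissue stripping".

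**The concern.** Two sentences describe the primary outcome measure and do not match word for word. The broader one could cover any parameter of the fluorescence curve. The sizing sentence fixes baseline as one side of the comparison but leaves the other side open: the post-osteotomy image, the post-stripping image, or each in turn. A one-tailed test needs a direction, and the objective and hypothesis speak only of change.

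If these choices were made after seeing data, the error rate could exceed 5%. If both steps had to show an effect, 20 patients might be too few. The half-enrolment recalculation sharpens the question, because it needs to know which difference it is sizing. Aim 2 also tunes image processing within the same study.

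**Working it through.** **Inputs.** From Section 11: difference 0.84 SD, one-tailed alpha 0.05, n = 20 plus 10. The type II error is printed as 0.80; it is read here as power 0.80, since 20 cannot be reproduced otherwise. Section 11 does not say whether 0.84 is in units of the raw SD or of the SD of within-patient change, so both are shown. With raw SD and within-patient correlation r (an assumption), the standardised paired effect is dz = 0.84/√(2(1−r)). This is 0.594 at r = 0 and 0.84 at r = 0.5, the latter coinciding with the SD-of-change reading.

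**The protocol's figure.** Two-sample normal formula: 2 × (1.645 + 0.842)² / 0.84² = 17.5, so 18 per group; the t version gives 19. A paired t test with dz = 0.594 also needs 19. Both are close to the stated 20. With dz = 0.84 a paired t test needs only 11.

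**Power under the open readings.** One contrast uses the paired noncentral t with noncentrality dz√n: for n = 20 and dz = 0.594 this is 2.66 against a critical value of 1.729, giving 82%. The rows for both contrasts come from simulation (100,000 replicates), assuming an equal 0.84 fall in both later states.

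| Reading | dz = 0.84: n = 20 / 30 / 40 | dz = 0.594: n = 20 / 30 / 40 |
|---|---|---|
| One contrast, one-tailed | 97.6% / 99.8% / >99.9% | 82% / 94% / 98% |
| One contrast, two-sided | 94.5% / 99% / 99.9% | 71% / 88% / 96% |
| Both contrasts, one-tailed | 96% / 99.6% / >99.9% | 71% / 89% / 96% |
| Both contrasts, two-sided | 90% / 99% / 99.9% | 57% / 80% / 92% |

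If either contrast may count and alpha is split (one-sided 0.025 each), 80% power per contrast needs 14 patients (dz = 0.84) or 25 (dz = 0.594).

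**Type I error.** One contrast and direction fixed beforehand: 0.05. Either contrast allowed to count without adjustment: 1 − P(Z₁ < 1.645, Z₂ < 1.645) = 0.088 at contrast correlation 0.5, or 0.068 at 0.9. Direction chosen after seeing the data: 0.05 + 0.05 = 0.10. The protocol proposes neither of these practices.

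**Whether the passages conflict.**
- *Outcome.* Section 3.0 reports that fluorescence imaging assessed bone perfusion in a porcine model, and Section 11 bases the TBBF sizing on the porcine study. In Section 6.7 this imaging is the only bone-perfusion measurement; the finger probe supplies the arterial input. The natural reading is that TBBF is the metric and fluorescence imaging its source.
- *Direction.* Hypothesis 1 speaks of vascular compromise and Aim 2 of low bone perfusion. With a one-tailed test, only a fall makes sense.
- *Image pair.* Stripping follows osteotomy, so baseline against the post-stripping image captures both steps. This is plausible but not forced by the text.

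**The case for a change.** The strongest case for a change is that the fault lies in the protocol itself. An analysis plan could define TBBF and the contrast, yet Sections 4.0 and 11 would still differ in wording. The planned recalculation also cannot be run without knowing which difference it concerns. Aligning the sentences would need no new procedure and, with the test kept one-tailed, would cost no power.

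Part of this stands. TBBF is named only in Section 11, and the second image is not identified. The rest does not carry far. Imx is an unused entry in an abbreviation list that also expands GDP as Good Clinical Practice; no section proposes to analyse it, so it is not a rival outcome. The 71% power for both contrasts at 20 patients needs a rule that both must succeed, zero correlation between repeated measurements in one patient, and equal falls after each step. The protocol states none of these. Ranking the contrasts, testing them in sequence or keeping Aim 2 tuning out of the primary test would be design choices, not corrections of an error.

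**Conclusion.** No change to the plan follows. What is missing is definition: the TBBF derivation, the second image and an explicit statement that a fall is expected. Analysts ordinarily settle this in a statistical analysis plan, which was not available here, and a sensible reading of the protocol already points to the answer. Carried out as one pre-fixed one-tailed test, the plan keeps its 5% error rate.

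The sample size is not put in doubt. For non-negative within-patient correlation, 30 evaluable patients give at least 88% power for a single contrast whether one- or two-sided, 89% if both contrasts had to succeed one-tailed, and 80% even if both had to succeed two-sided. These figures rest on the 0.84 SD effect being true and on all 30 patients being evaluable. If only 20 are evaluable and the raw-SD, zero-correlation reading holds, the single one-tailed contrast still has 82%. The difference in wording between Sections 4.0 and 11 is editorial, in a study that Section 3.0 presents as gathering pilot data.

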5.0 Study Intervention/Investigational Agent

5.1 Description:

ICG fluorescence imaging has been used to assess tissue perfusion in vivo in real-time in arterial and lymphatic perfusion imaging^{25, 26}, osseous flap perfusion imaging²⁷. ICG has been approved for clinical use by the FDA since 1959. The dynamic fluorescence imaging systems used in this study will be the Pentero surgical microscope (Zeiss, Germany), SPY Elite (Novodaq/Stryker), or SPY PHI (Novodaq/Stryker). Both are publicly available imaging systems that can be used to assess tissue perfusion in real time in the operating room. The systems have a multi-directional imaging arm which contains a near-infrared light source that illuminates the fluorescent agent within the tissues, an HD video camera that captures the intensity of fluorescent marker in real-time, and software that allows the user to capture relative and absolute perfusion values within the surgical field. This product has been FDA approved for use to monitor blood flow, plastic surgery, microsurgery, reconstructive surgery, gastrointestinal imaging and coronary bypass surgery.

This study is *neither a drug nor a device trial*. Patients will be administered FDA approved ICG through intravenous injection and imaged by a FDA approved surgical microscope (Pentero, SPY Elite, or SPY PHI) which is 0.5 meter away from the subject. Both ICG fluorescence and the two imaging systems have been used for routine clinical practice for many years. Figure (a) shows the Schematic sketch of the imaging systems. ICG fluorescence imaging utilizes intravenously injected ICG which is a fluorecent dy that is FDA-approved for clinical use, illuminated with near infrared light. The ICG dye is indirectly activated and the dynamic fluorescence due to bone perfusion can be captured by a video rate imaging system.

This study is similar to STUDY00031575 in terms of methodology with a nearly identical intervention. That study is approved and active, but in a different patient population, both of which are highly clinically relevant.

5.2 Subject Compliance Monitoring

Subjects participate in a "one-time" event (i.e., surgery) as part of this study and are monitored through the in-patient surgical service during the time of their participation.

5.3 Receipt of Drug Supplies

Indocyanine green (ICG)/drape kits used in this study are purchased from Stryker. Each kit includes 25mg ICG, 10cc saline and a sterile drape. Kits will be delivered to DHMC Investigational Drug Services and to each relying site when needed who will count and verify that the shipment contains all of the items noted in the shipment inventory. Any damaged kits will be documented in study files and destroyed on site. This is standard of care for ICG/drape kits used clinically in non-research indications.

5.4 Storage

ICG will be stored in a locked temperature controlled room, as is standard of care for ICG/drape kits used clinically in non-research indications.

5.5 Dispensing of Study Drug

Once agent assignment is performed, research staff will transport ICG in its original package to the operating room. The surgeon or anesthesiologist will prepare the solution for injection per instructions from the Stryker. 0.1mg/kg ICG will then be administered per study protocol.

5.6 Drug Accountability

A member of the study team will document the amount of ICG administered and any amount remaining in the institution's electronic medical record.

5.7 Return or Destruction of Study Drug

ICG is FDA approved for routine clinical practice. No return or destruction of study drug is needed for this study.

6.0 Procedures Involved*

This is a prospective non-randomized clinical trial which will assess bone perfusion using

ICG fluorescence imaging at several step in the surgical procedure to assess the effect of these steps on bone perfusion. This is neither a drug nor a device trial. Patients will be administered FDA approved ICG through intravenous injection and imaged using an FDA approved surgical microscope (Pentero, SPY Elite, or SPY PHI).

6.1 Patient selection

Consecutive patients 18 years of age or older who present to DHMC and are scheduled to undergo a lower extremity amputation (either below knee, through knee or above knee) will be considered for study enrollment.

6.2 Inclusion Criteria

The following criteria must be met by subjects to be eligible for study enrollment

- a. Patients 18 years of age or older
- b. Scheduled for a lower extremity amputation (either below knee, through knee or above knee)
- c. Provision of informed consent

6.3 Exclusion Criteria

The following criteria would exclude a subject from study enrollment

- a. Iodine allergy
- b. Pregnant or breastfeeding women

6.4 Subject Recruitment and Retention

Participation in this research requires informed consent according to Institutional Review Board (IRB) guidelines and a signed IRB-approved Consent Form as the means of documenting this understanding. Potential recruits are instructed that their participation is completely voluntary and that their medical care will not be altered in any way should they elect not to participate at any time prior to surgery. Subjects are recruited from patients presenting or referred to Orthopedic Department at Dartmouth-Hitchcock Medical Center for treatment and meeting protocol inclusion criteria. Potential subjects will be approached by a member of their care team to gauge interest about participation in research prior to being approached by a member of the study team. Subjects will be invited to participate in this study by a member of the Orthopaedic Department, which will occur either at the time of consultation with the surgeon about the candidate's standard-of-care procedures or at another time agreed to by the potential participant, the candidate's surgeon and/or [name] and/or [name] or their designee. No advertisements or other promotional material will be used. No finder fees or recruitment incentives will be offered. Women of child bearing potential are eligible for enrollment into this study because ICG administration is not considered to present any additional risk for these women. The study will exclude women who are pregnant or breast-feeding as indicated in the exclusion criteria. Women of child-bearing potential, if asked to participate, will be

given a pregnancy test at no cost to confirm pregnancy status before administration of ICG.

Eligible patients regardless of ethnicity or health status, will be identified and recruited subject to inclusion and exclusion criteria above. Patients who meet eligibility criteria will be asked to participate in the trial. If they agree written informed consent will be obtained from the patient or their healthcare proxy. To obtain informed consent, study personnel (surgeon or research coordinator) will adhere to the following procedures: (1) present study information in a manner that is understandable to the patient; (2) discuss the study with the patient and answer any questions; (3) allow the patient an opportunity to discuss participation with their family; (4) confirm that the patient understands the risks and benefits of participating in the study and that their participation is voluntary; (5) complete the consent process and obtain signatures from the patient and research team. The process of obtaining and documenting informed consent forms will be completed in accordance with local Good Clinical Practice (GCP) recommendations.

If the research team member obtaining consent is at all unsure about the patient's ability to consent, s/he will consult with the study PI.

A legally authorized representative (LAR) with reasonable knowledge of the potential participant will be approached to consent on the patient's behalf if the patient cannot adequately answer at least 2 questions and it is determined that the patient's level of cognition is not likely to change before surgery.

The choice of LAR will follow standard procedures. The following with be approached in this order of priority:

- Legal guardian
- Proxy (health care agent) named in an advance directive or durable power of attorney for health care
- Family member or other surrogate identified by the state law on health care decisions. Guidance will be provided to assist the LAR in making the consent decision. They will advised to base the decision on the participant's expressed wishes, or, if these are not known, what they believe the participant would have desired under the circumstances of the injury, their beliefs and values. If the LAR does not know what the participant would have wanted, the LAR will advised to base the decision with the participant's best interest in mind. They will be asked to carefully consider how much leeway the participant would likely give the LAR in making the choice about participation in the study.

Recognizing that consent is an ongoing process, the study team will encourage the participants to ask additional questions that may arise during the course of their participation in the study.

